11. MEASUREMENT OF EFFECT

11.1 Antitumor Effect – Solid Tumors

For the purposes of this study, participants should be re-evaluated for response every 8 weeks. In addition to a baseline scan, confirmatory scans should also be obtained 8 weeks following initial documentation of objective response.

Response and progression will be evaluated in this study using the modified Response Evaluation Criteria in Solid Tumors (RECIST) guidelines for mesothelioma (version 1.1).⁴⁴

Tumor thickness perpendicular to the chest wall or mediastinum is measured in two positions at three separate levels on transverse cuts of a CT scan. The sum of the six measurements defines a pleural unidimensional measure. Transverse cuts at least 1 cm apart and related to anatomical landmarks in the thorax are chosen to allow reproducible assessment at later time points. If measureable tumor is present, transverse cuts in the upper thorax, above the level of division of the main bronchi are preferred. At reassessment, pleural thickness is measured at the same position at the same level. This is not necessarily the greatest tumor thickness at that level. Nodal, subcutaneous and other bidimensionally measurable lesions are measured unidimensionally as per the RECIST 1.1 criteria. Unidimensional measurements are added to obtain the total tumor measurement.

11.1.1 Definitions

Evaluable for Target Disease response. Only those participants who have measurable disease present at baseline, have received at least one cycle of therapy, and have had their disease re-evaluated will be considered evaluable for target disease response. These participants will have their response classified according to the definitions stated below. (Note: Participants who exhibit objective disease progression prior to the end of cycle 1 will also be considered evaluable.)

Evaluable Non-Target Disease Response. Participants who have lesions present at baseline that are evaluable but do not meet the definitions of measurable disease, have received at least one cycle of therapy, and have had their disease re-evaluated will be considered evaluable for non-target disease. The response assessment is based on the presence, absence, or unequivocal progression of the lesions.

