13.3 Analysis of Primary and Secondary Endpoints

The primary and secondary analyses will include all eligible patients who started assigned therapy. The exception to this includes the planned analysis of toxicity data, which will include all patients who received study drug regardless of eligibility. Response will be assessed using the modified RECIST criteria for mesothelioma; toxicity will be graded using CTCAE v. 4.03.

For the analysis of the response efficacy measures, participants will be censored if they are alive and without disease progression at the date of the last disease evaluation. In the case of OS, participants will be censored if they are living at the date last known alive.

Time-to-event data, such as PFS and OS, will be estimated using the Kaplan-Meier method, and Cox proportional hazards models will be used to estimate hazard ratios. Comparisons of groups will be made using the logrank test and Cox modeling.

Categorical data, such as response rates (CR+PR) and toxicity, will be compared using Fisher's exact tests with a one-sided type I error rate of 10%; multivariable logistic regression modeling will be used to adjust for the effect of any covariates that are associated with these categorical outcomes. Though none are currently planned, any continuous outcomes will be analyzed using Wilcoxon rank sum test, and multivariable linear regression models may be used to adjust for multiple associations with outcome.

Modeling procedures will implement backward selection; variables significant at the 0.10 level in the univariate setting will be chosen for inclusion in an initial full model, and at each step the least significant variable will be removed from the model. Only those covariates with p<0.05 will remain in any final models, unless there are factors identified by the study team as crucial to model interpretation.

Point estimates of all endpoints will be accompanied by the corresponding two-sided 80% confidence intervals. The method of Atkinson and Brown will be used for the estimation of the confidence interval for response.

In the event that there are missing data, no imputation of the missing data will be conducted. We will assume that data are missing at random and will conduct all analyses as originally planned because we do not anticipate an excess of missing data.

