13.4.2 Evaluation of the Primary Efficacy Endpoint

All eligible participants included in the study will be assessed for response, even if there are major protocol therapy deviations. Each participant should be assigned one of the following categories: 1) complete response, 2) partial response, 3) stable disease, 4) progressive disease, 5) early death from malignant disease, 6) early death from toxicity, 7) early death because of other cause, or 9) unknown (not assessable, insufficient data). By arbitrary convention, category 9 usually designates the "unknown" status of any type of data in a clinical database.

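### Could participants of unknown response drop out of the primary response-rate denominator?

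*Combined protocol and SAP*

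**What the plan says.** Section 13 sets a Simon two-stage design. Accrual continues if 4 or more of the first 19 patients respond, and success needs 10 or more responses among all 40. The null rate is 16% and the target 35%, with stated early stopping of 0.64 under the null, 90% power and one-sided type I error of 0.08. A responder is a patient with a complete or partial response.

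Section 13.3 gives the analysis set: "The primary and secondary analyses will include all eligible patients who started assigned therapy". It defines response rates as CR+PR. On missing data it says "no imputation of the missing data will be conducted. We will assume that data are missing at random", and the sentence goes on to say that the analyses will be run as planned. For the interval: "The method of Atkinson and Brown will be used for the estimation of the confidence interval for response", at the two-sided 80% level.

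Section 13.4.2 adds: "All eligible participants included in the study will be assessed for response, even if there are major protocol therapy deviations". Each participant gets one category. Early deaths have three of their own (5 to 7), and the last is "9) unknown (not assessable, insufficient data").

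Section 11.1.1 is narrower. It begins "Only those participants who have measurable disease present at baseline" and requires that they "have received at least one cycle of therapy, and have had their disease re-evaluated will be considered evaluable for target disease response". A note softens this: "Participants who exhibit objective disease progression prior to the end of cycle 1 will also be considered evaluable".

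**The concern.** Three features together look like a gap in the primary endpoint. The unknown category is listed but not assigned to non-response. Section 11.1.1 classifies response only in re-evaluated participants, whereas Section 13.4.2 wants a category for everyone. The missing-at-random sentence in Section 13.3 makes no exception for response.

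The exposed participant is specific. Early deaths have their own categories and early objective progression is evaluable. What remains is someone who stops before the first 8-week scan through clinical decline or withdrawal and is never imaged again. Section 11.1.4.4 calls the first of these symptomatic deterioration, but Section 13.4.2 has no matching category, so only the unknown one fits. Clinical decline predicts non-response, so missing at random is implausible for that group.

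If such participants were dropped, the reported ORR and its 80% interval would rise. A trial with 9 responses, which fails its own rule, could then publish an interval lying above the 16% control rate.

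A related point is that Section 13.3 excludes treated participants found ineligible, while Section 13 fixes its cutoffs at 19 and 40.

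**Working it through.** **Inputs.** From Section 13: n1 = 19, continue at 4 or more; n2 = 21, success at 10 or more of 40; p0 = 0.16, p1 = 0.35. The documents give no not-assessable rate for this trial, so 2, 4 or 6 of 40 are assumed, all taken as true non-responders.

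**The plan's own figures.**
- Early stopping = P(X1 ≤ 3 | 19, 0.16) = 0.638 (stated 0.64).
- Success probability = Σ over x ≥ 4 of P(X1 = x | 19, p) × P(X2 ≥ 10 − x | 21, p). At p = 0.16 this is 0.0824 (stated 0.08); at p = 0.35 it is 0.901 (stated 90%).

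**Effect on the decision.** The rule counts responses. An unknown is not a response, so removing one leaves the count as it was. The 4/19 and 10/40 rules keep type I error 0.0824 and power 0.901 whatever the number of unknowns.

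**Effect on the estimate, if unknowns were dropped.** The lower limit solves P(continue and total ≥ s | p) = 0.10. The upper limit solves P(stop, or continue with total ≤ s | p) = 0.10. Outcomes are ordered by stage and then total, used here for the interval method named in Section 13.3. Losses are split equally between stages.

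| Dropped | ORR, 10 responses | 80% interval | ORR, 9 responses | 80% lower limit |
|---|---|---|---|---|
| 0 | 10/40 = 25.0% | 16.6–36.9% | 9/40 = 22.5% | 14.8% |
| 2 | 10/38 = 26.3% | 17.5–38.6% | 9/38 = 23.7% | 15.6% |
| 4 | 10/36 = 27.8% | 18.5–40.6% | 9/36 = 25.0% | 16.5% |
| 6 | 10/34 = 29.4% | 19.7–42.7% | 9/34 = 26.5% | 17.5% |

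With 9 of 36 the lower limit runs from 16.1% to 17.1% depending on the stage of the losses, so it exceeds 16% in every split. With 9 of 37 it runs from 15.7% to 16.5%.

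**How likely that clash is.** It needs the trial to reach stage 2 and end with exactly 9 responses: probability 0.06 at a true rate of 16%, about 0.10 at 20% to 25%, and 0.02 at 35%. It also needs at least 3 or 4 unknowns and an analyst who sets the stated population aside.

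**What the text requires.** The numerator is CR+PR (Sections 13 and 13.3). The denominator is all eligible treated patients (Section 13.3). A participant of unknown response belongs to the second set and not the first, so the ORR is determined without a further rule. The missing-data sentence ends by keeping the planned analyses, and the planned analysis uses that denominator. No section makes the Section 11.1.1 group an ORR denominator or provides for replacing unevaluable participants.

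**The case for a change.** The strongest contrary case is that naming a population does not say how its unknown outcomes are scored. Section 11.1.1 uses restrictive wording, and an analyst could treat unknown as missing and delete it under Section 13.3. Section 2.4.3 shows that the group need not be empty: with the same two drugs in lung cancer, 10 of 63 were not evaluable. That source kept them in, giving 17/63 = 27.0% rather than 17/53 = 32.1%. The same share here would be 40 × 10/63 ≈ 6 participants.

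Part of this stands. No sentence labels the unknown category as non-response, and missing at random is a poor description of clinical decline. But Section 11.1.1 reads naturally as a measurement definition: it says who can be graded on target lesions, and those who cannot be graded become unknown under Section 13.4.2. The lung cancer figure may also overstate the group, because that evaluable set included deaths without a follow-up scan, which here have their own categories. Section 11.1.4.4 asks for every effort to document progression after stopping. The study calendar, although its table is broken in the text, appears to schedule imaging at the off-treatment visit.

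Reading the final cutoff as 25% of evaluable patients would do more harm: type I error would be 0.116 if an assumed 10% were unknown. Section 13 does not permit that reading, since it states a count among all 40.

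On ineligible participants, removing one per stage with the cutoffs kept would give power 0.864 and type I error 0.061. Removing one from stage 2 only would give 0.890 and 0.073. These rest on assumed removals, and eligibility is confirmed before registration (Section 4.1). Counting all treated participants for the decision while reporting an eligible-only ORR has its own cost: one ineligible responder would put success at 10/40 beside a reported 9/39 = 23.1%. That is a debatable trade-off, not a correction.

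**Conclusion.** No change is needed. Followed as written, the plan gives an ORR of CR+PR over all eligible treated participants, with unknown responses counting against the treatment. The missing sentence is a detail that analysts would fill the same way from Sections 13, 13.3 and 13.4.2. The go/no-go decision does not depend on it.

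The exposure is confined to the reported estimate, under a reading that overrides the stated population: 1.3, 2.8 or 4.4 percentage points at 10 responses if 2, 4 or 6 of 40 were dropped. Those counts are assumptions, as is treating every unknown as a non-responder. The interval limits also depend on the ordering used, but the point estimates do not. The plan does not make the 80% interval a success criterion, so even the 9-response case would leave an awkward report and not a wrong decision. The ineligibility question is separate and gives no clear reason to alter the cutoffs or the analysis set.

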11.1.2 Disease Parameters

Measurable disease. Measurable lesions are defined as those that can be accurately measured in at least one dimension of at least 10 mm in diameter or thickness with CT scan, MRI, or calipers by clinical exam. All tumor measurements must be recorded in millimeters (or decimal fractions of centimeters).

Note: Tumor lesions that are situated in a previously irradiated area might or might not be

considered measurable.

Malignant lymph nodes. To be considered pathologically enlarged and measurable, a lymph node must be ≥ 15 mm in short axis when assessed by CT scan (CT scan slice thickness recommended to be no greater than 5 mm). At baseline and in follow-up, only the short axis will be measured and followed.

Non-measurable disease. All other lesions (or sites of disease), including small lesions (longest diameter <10 mm or pathological lymph nodes with \geq 10 to <15 mm short axis), are considered non-measurable disease. Bone lesions, leptomeningeal disease, ascites, pleural/pericardial effusions, lymphangitis cutis/pulmonitis, inflammatory breast disease, abdominal masses (not followed by CT or MRI), and cystic lesions are all considered non-measurable.

Note: Cystic lesions that meet the criteria for radiographically defined simple cysts should not be considered as malignant lesions (neither measurable nor non-measurable) since they are, by definition, simple cysts.

'Cystic lesions' thought to represent cystic metastases can be considered as measurable lesions, if they meet the definition of measurability described above. However, if non-cystic lesions are present in the same participant, these are preferred for selection as target lesions.

Target lesions. All measurable lesions up to a maximum of 2 lesions per organ and 5 lesions in total, representative of all involved organs, should be identified as **target lesions** and recorded and measured at baseline. Target lesions should be selected on the basis of their size (lesions with the longest diameter), be representative of all involved organs, but in addition should be those that lend themselves to reproducible repeated measurements. It may be the case that, on occasion, the largest lesion does not lend itself to reproducible measurement in which circumstance the next largest lesion which can be measured reproducibly should be selected. A sum of the diameters (longest for non-nodal lesions, short axis for nodal lesions) for all target lesions will be calculated and reported as the baseline sum diameters. If lymph nodes are to be included in the sum, then only the short axis is added into the sum. The baseline sum diameters will be used as reference to further characterize any objective tumor regression in the measurable dimension of the disease.

Non-target lesions. All other lesions (or sites of disease) including any measurable lesions over and above the 5 target lesions should be identified as **non-target lesions** and should also be recorded at baseline. Measurements of these lesions are not required, but the presence, absence, or in rare cases unequivocal progression of each should be noted throughout follow up.

11.1.3 Methods for Evaluation of Disease

All measurements should be taken and recorded in metric notation using a ruler, calipers,

or a digital measurement tool. All baseline evaluations should be performed as closely as possible to the beginning of treatment and never more than 4 weeks before the beginning of the treatment.

The same method of assessment and the same technique should be used to characterize each identified and reported lesion at baseline and during follow-up. Imaging-based evaluation is preferred to evaluation by clinical examination unless the lesion(s) being followed cannot be imaged but are assessable by clinical exam.

Clinical lesions. Clinical lesions will only be considered measurable when they are superficial (*e.g.*, skin nodules and palpable lymph nodes) and ≥ 10 mm in diameter as assessed using calipers (*e.g.*, skin nodules). In the case of skin lesions, documentation by color photography, including a ruler to estimate the size of the lesion, is recommended.

Chest x-ray. Lesions on chest x-ray are acceptable as measurable lesions when they are clearly defined and surrounded by aerated lung; however, CT is preferable.

Conventional CT and MRI. This guideline has defined measurability of lesions on CT scan based on the assumption that CT thickness is 5mm or less. If CT scans have slice thickness greater than 5 mm, the minimum size of a measurable lesion should be twice the slice thickness. MRI is also acceptable in certain situations (*e.g.* for body scans).

Use of MRI remains a complex issue. MRI has excellent contrast, spatial, and temporal resolution; however, there are many image acquisition variables involved in MRI, which greatly impact image quality, lesion conspicuity, and measurement. Furthermore, the availability of MRI is variable globally. As with CT, if an MRI is performed, the technical specifications of the scanning sequences used should be optimized for the evaluation of the type and site of disease. Furthermore, as with CT, the modality used at follow-up should be the same as was used at baseline and the lesions should be measured/assessed on the same pulse sequence. It is beyond the scope of the RECIST guidelines to prescribe specific MRI pulse sequence parameters for all scanners, body parts, and diseases. Ideally, the same type of scanner should be used and the image acquisition protocol should be followed as closely as possible to prior scans. Body scans should be performed with breath-hold scanning techniques, if possible.

FDG-PET. While FDG-PET response assessments need additional study, it is sometimes reasonable to incorporate the use of FDG-PET scanning to complement CT scanning in assessment of progression (particularly possible 'new' disease). New lesions on the basis of FDG-PET imaging can be identified according to the following algorithm:

(a) Negative FDG-PET at baseline, with a positive FDG-PET at follow-up is a sign of PD based on a new lesion.

(b) No FDG-PET at baseline and a positive FDG-PET at follow-up: If the positive FDG-PET at follow-up corresponds to a new site of disease confirmed by CT, this is PD. If the positive FDG-PET at follow-up is not confirmed as a new site of disease on CT, additional follow-up CT scans are needed to determine if there is truly progression occurring at that site (if so, the date of PD will be the date of the initial

abnormal FDG-PET scan). If the positive FDG-PET at follow-up corresponds to a pre-existing site of disease on CT that is not progressing on the basis of the anatomic images, this is not PD.

(c) FDG-PET may be used to upgrade a response to a CR in a manner similar to a biopsy in cases where a residual radiographic abnormality is thought to represent fibrosis or scarring. The use of FDG-PET in this circumstance should be prospectively described in the protocol and supported by disease-specific medical literature for the indication. However, it must be acknowledged that both approaches may lead to false positive CR due to limitations of FDG-PET and biopsy resolution/sensitivity.

Note: A 'positive' FDG-PET scan lesion means one which is FDG avid with an uptake greater than twice that of the surrounding tissue on the attenuation corrected image.

PET-CT. At present, the low dose or attenuation correction CT portion of a combined PET-CT is not always of optimal diagnostic CT quality for use with RECIST measurements. However, if the site can document that the CT performed as part of a PET-CT is of identical diagnostic quality to a diagnostic CT (with IV and oral contrast), then the CT portion of the PET-CT can be used for RECIST measurements and can be used interchangeably with conventional CT in accurately measuring cancer lesions over time. Note, however, that the PET portion of the CT introduces additional data which may bias an investigator if it is not routinely or serially performed.

MIBG (meta-iodobenzylguanidine).The following is recommended, to assure high quality images are obtained.

Patient preparation: Iodides, usually SSKI (saturated solution of potassium iodide), are administered to reduce thyroidal accumulation of free radioiodine, preferably beginning the day prior to injection and continuing for 3 additional days (4 days total). For infants and children, one drop t.i.d. is sufficient, for adolescents 2 drops t.i.d., and for adults 3 drops t.i.d. Participants and/or parents are asked about exposure to potential interfering agents. If none is noted, an indwelling intravenous line is established. The dose of MIBG is administered by slow intravenous injection over 90 seconds.

Images from the head to the distal lower extremities should be obtained.

I-123MIBG scintigraphy is performed to obtain both planar and tomographic images.

Planar: Anterior and posterior views from the top of the head to the proximal lower extremities are obtained for 10 minutes at 24 hours and occasionally at 48 hours following injection of 10 mCi/1.7 square meters of body surface area (~150 μ Ci/kg, maximum 10 mCi). Anterior views of the distal lower extremities are adequate. A large field of view dual head gamma camera with low energy collimators is preferred.

SPECT: Most participants receiving I-123 MIBG also undergo SPECT at 24 hours, using a single or multi-headed camera with a low energy collimator. The camera is rotated through 360 degrees, 120 projections at 25 seconds per stop. Data are reconstructed using filtered back projections with a Butterworth filter and a cut off frequency of 0.2-0.5. SPECT/CT may be performed at institutions with this capacity.

Ultrasound. Ultrasound is not useful in assessment of lesion size and should not be used as a method of measurement. Ultrasound examinations cannot be reproduced in their entirety for independent review at a later data and, because they are operator dependent, it cannot be guaranteed that the same technique and measurements will be taken from one assessment to the next. If new lesions are identified by ultrasound in the course of the study, confirmation by CT or MRI is advised. If there is concern about radiation exposure from CT, MRI may be used instead of CT in selected instances.

Endoscopy, Laparoscopy. The utilization of these techniques for objective tumor evaluation is not advised. However, such techniques may be useful to confirm complete pathological response when biopsies are obtained or to determine relapse in trials where recurrence following complete response (CR) or surgical resection is an endpoint.

Tumor markers. Tumor markers alone cannot be used to assess response. If markers are initially above the upper normal limit, they must normalize for a participant to be considered in complete clinical response. Specific guidelines for both CA-125 response (in recurrent ovarian cancer) and PSA response (in recurrent prostate cancer) have been published [*JNCI* 96:487-488, 2004; *J Clin Oncol* 17, 3461-3467, 1999; *J Clin Oncol* 26:1148-1159, 2008]. In addition, the Gynecologic Cancer Intergroup has developed CA-125 progression criteria which are to be integrated with objective tumor assessment for use in first-line trials in ovarian cancer [*JNCI* 92:1534-1535, 2000].

Cytology, Histology. These techniques can be used to differentiate between partial responses (PR) and complete responses (CR) in rare cases (*e.g.*, residual lesions in tumor types, such as germ cell tumors, where known residual benign tumors can remain).

The cytological confirmation of the neoplastic origin of any effusion that appears or worsens during treatment when the measurable tumor has met criteria for response or stable disease is mandatory to differentiate between response or stable disease (an effusion may be a side effect of the treatment) and progressive disease.

